## **5.2 Parent Education about Rotavirus Vaccines and the Study**

Parents approached for this study will be educated about the two licensed rotavirus vaccines (RV1 and RV5) and informed that the AAP and ACIP routinely recommend rotavirus vaccines for infants and do not express a preference for RV1 or RV5. We will explain that their infant may be randomized to a vaccine type different from the vaccine given at their primary care practice. The parent will also be informed that RV1 is a two dose vaccine series and RV5 is a three dose vaccine series and that if they choose to have their infant participate in the study, their infant will need to complete the series with the same vaccine type (all RV1 or all RV5). RV1 is to be administered orally in a 2-dose series, with doses administered at ages 2 and 4 months. RV5 is to be administered orally in a 3-dose series, with doses administered at ages 2, 4, and 6 months. The minimum age for dose 1 of rotavirus vaccine is 6 weeks; the maximum age for dose 1 is 14 weeks and 6 days. The minimum interval between doses of rotavirus vaccine is 4 weeks and there is no maximum interval set. All doses should be administered by age 8 months and 0 days. The parent of infants who are randomized to receive rotavirus vaccines without other childhood vaccines will be informed that since the purpose of the study is to study the effects of rotavirus vaccine, their infant will wait to receive the rotavirus vaccine until two weeks or more after other routinely administered immunizations or will not receive their other recommended vaccines until two weeks or more after their rotavirus vaccine. If the child is receiving routine immunizations after the rotavirus vaccine, every effort will be made for the infant to receive these vaccines within the recommended ACIP schedule for vaccines routinely recommended at 2 months of age (DTaP, Hib, Prevnar, Hepatitis B and IPV vaccine). The parents of infants who are randomized to receive rotavirus vaccines with other recommended vaccines will be informed of this for their planning and provided with a

letter for their pediatrician. These infants will still be recommended to have a 2-month well child check-up, but will be asked not to receive 2-month vaccines at this visit. Children receiving other childhood vaccines as part of the study will receive the following vaccines Pentacel (DTaP, Hib and IPV combination), Prevnar (PCV13) and HBV, in addition to the rotavirus vaccine. If one of these is not available we will replace it with another equivalent licensed vaccine. All vaccines administered as part of the study will be documented for the parent and child's health care provider. This information will be faxed to the provider. The vaccines administered will be documented in EPIC, in IMPACT (the Ohio State Registry) and in letter form with copies of the EPIC documentation to the parent and provider of the enrolled child.

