### Subject Exclusion Criteria

Infants will not be eligible if any of the below conditions apply:

1. gestational age of <37 weeks
2. infant unable to fast for 4 hours prior to MRI procedure
3. receipt of any vaccine except initial HBV (must have at least 28 days between HBV and Visit 1 to be included)
4. history of severe allergic reaction to HBV vaccine
5. contraindications for any of the routine vaccines
  - a. Severe Combined Immune Deficiency
  - b. history of intussusception
6. precautions for either RV1 or RV5 (may interfere with study outcomes)
  - a. altered immunocompetence
    - i. infants with primary and acquired immunodeficiency states, cellular immunodeficiency, hypogammaglobulinemic and dysgammaglobulinemic states
    - ii. infants with blood dyscrasias, leukemia, lymphomas, or other malignant neoplasms affecting the bone marrow or lymphatic system
    - iii. infants on immunosuppressive therapy (including high-dose systemic corticosteroids)
    - iv. infants who are HIV-exposed or infected
  - b. acute gastroenteritis
  - c. moderate or severe acute illness with or without fever
  - d. pre-existing chronic gastrointestinal diseases (e.g., congenital malabsorption syndromes, Hirschsprung's disease, or short-gut syndrome)
  - e. infants with spina bifida or bladder exstrophy (latex rubber is contained in the RV1 oral applicator)
7. sensitivity to latex (latex rubber is contained in the RV1 oral applicator)
8. febrile illness within previous 14 days (axillary temperature of 100.4° F or higher)
9. history of vomiting (forceful expulsion of partially digested milk/food) within 24 hours prior to Visit 1 and/or diarrhea (3 watery stools) within 14 days of Visit 1
10. receipt of any steroids, immunoglobulins, other blood products/transfusion
11. receipt of non-steroidal anti-inflammatory drugs in previous 72 hours (may affect cytokine response)
12. receipt of an antipyretic medication (acetaminophen or ibuprofen) within 72 hours prior to the first dose of rotavirus vaccine or is already planning to administer a prophylactic antipyretic medication on the day of and the day following vaccination (this exclusion does not apply if the caretaker indicates he/she might administer antipyretics after vaccination to reduce a fever)
13. is enrolled or plans to enroll in another clinical trial while participating in this study (observational studies are allowed)

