## **5 STUDY SCHEDULE ( See Appendix 1)**

### **5.1 Recruitment and Enrollment**

Recruitment will be done by our study personnel through the Pediatric Primary Care (PPC) Clinic at CCHMC and through study advertisement at CCHMC targeted towards our employee e-mail system and database of past research participants who have agreed to be e-mailed for future studies. Any written communication provided to the potential subjects' parents/legal guardians about the study will be submitted to the IRB for their approval before study initiation.

We routinely conduct studies through the PPC and our research personnel are present in the clinic. We will review the patients scheduled and will identify those who are age eligible for the study. The medical

record for those age-eligible will be screened to identify children who would not be eligible for the study (exclusion criteria). Parents of potentially eligible infants will be approached to discuss participation in the study. If interested, informed consent will be obtained before giving instructions and scheduling Visit 1. After consent is obtained, infant will be randomized into one of four study groups.

For recruitment of infants of CCHMC employees and through our research database, the interested parent will call our study line. Relatives of study personnel will be excluded from participation as is standard procedure. Study personnel will discuss the study by phone. Subjects will be screened by medical history from the parent. If eligible and interested, a meeting time will be arranged prior to Visit 1 to obtain informed consent. The infant's primary care provider will be contacted to determine if the infant is healthy and to inform the primary care provider of the study after informed consent and prior to Visit 1. Parents will be informed that their decision to participate or not to participate in the study will not have any effect on them as an employee.

Because the infants to be enrolled will be healthy and will be receiving a licensed vaccine that is approved for use in this population, no additional screening will be necessary. No baseline laboratory screening will be performed prior to enrollment. Screening records will be kept to document the reason why a subject was screened but failed entrance criteria. If a parent chooses not to agree to the study, we will ask for a reason and it will be documented.

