## 5.3 Study Visits

### Enrollment/Recruitment Visit

- review inclusion/exclusion criteria and medical history
- obtain informed consent
- obtain a release to get medical information from the primary care provider
- collect contact information including the primary care provider of infant and the date of 2 month check up if known
- if refuses study, record refusal reason on screening log
- sample collection instructions
- distribute sample collection supplies
- review MRI and ultrasound prep
- randomize to study group and inform parent of result of all routine vaccines or rotavirus vaccine alone (not specific rotavirus vaccine type)
- schedule visit 1  
give written instructions for Visit 1 to parent (Appendix 5) **Reminder Call 1 (day prior to Visit 1)**
- review sample collection instructions
- review MRI/ultrasound prep  
review time, date and location of Visit 1 **Visit 1 (Day 0-Vaccine Administration)**
- contact information will be reviewed and updated if necessary
- inclusion and exclusion criteria will be reviewed to determine if child still meets criteria for study
- temperature will be recorded prior to immunization; axillary temperature must be <100.4° F prior to administration of vaccines
- breast milk specimen brought from home if mother is breast feeding or can be collected at the visit if needed
- saliva specimen collected for human blood group antigen testing
- baseline stool specimen (brought from home) before receiving the rotavirus vaccine
- MRI to assess intestinal anatomy and motility
- Ultrasound of abdomen to assess intestinal anatomy
- baseline blood specimen for cytokine testing and maternal antibody testing (IgG)
- The Vaccine Information Sheet (VIS) will be provided to parents/guardians for all vaccines administered.
- The study product administrator, who is licensed to administer the vaccine (e.g., MA, LPN, RN, NP, PA, or MD), will orally administer the rotavirus vaccine as indicated in the randomization code
  - if the infant vomits after receiving the vaccine, in accordance with AAP and ACIP recommendations, the vaccine will not be readministered but time of vaccine administration and vomiting will both be documented.

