## 6 STUDY PROCEDURES

### 6.1 Rotavirus Vaccine Randomization and Administration

Infants will be randomized to receive 1) RV1 alone, 2) RV5 alone, 3) RV1 with routine immunizations (DTaP, Hib, PCV13, HBV and IPV or 4) RV5 with routine immunizations prior to Visit 1. They will receive the vaccination(s) after the MRI/Ultrasound is completed at Visit 1.

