### APPENDIX 1. STUDY VISITS AND PROCEDURES

		Study Days															
	Recruitment/ Enrollment	-1	0	1	2	3	4	5	6	7	8	9	10	11	12	13	14
Visit	Recruitment		1					2									3
Age	<11wks		6 wks to- 12 wks, 6 days														
Informed Consent	X																
Demographics	X		X					X									X
Medical History	X		X					X									X
Inclusion/Exclusion Criteria	X	X	X					X									X
Explain & Distribute Memory Aide			X					X									
Axillary Temperature			X	X	X	X	X	X	X	X	X	X	X	X	X	X	X
Reactogenicity			X	X	X	X	X	X	X	X	X	X	X	X	X	X	X
Stool Instructions	X	X						X						X			
Supplies Distributed	X							X									
Review MRI Prep	X	X				X											
Schedule Appointment	X		X					X									
Reminder Call		X				X								X			
Infant Stool Collection			X	X	X	X	X	X	X	X	X	X	X	X	X	X	X
Randomized	X		X														
MRI			X					X									
Ultrasound			X					X									
Stool Submission			X					X									X
Memory Aid Review			X					X						X			X
Blood Obtained			X					X									
Breast Milk Sample			X														
Saliva Sample			X														
Vaccination			One of Four Groups														
Case Report Form	X		X					X						X			X
Vaccination Record			X														X
Parent Satisfaction																	X

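### Section 5.2 allows routine vaccines before rotavirus vaccine in the RV-alone arms, but exclusion 3, re-checked at Visit 1 after randomisation, makes an infant vaccinated in that order ineligible

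*Combined protocol and SAP*

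**What the plan says.** Section 5.2 gives parents of infants randomised to RV alone two possible orders. In the first, "their infant will wait to receive the rotavirus vaccine until two weeks or more after other routinely administered immunizations". In the second, the other vaccines follow rotavirus vaccine by at least two weeks. For the with-routine arms, 5.2 asks parents to keep the 2-month well-child visit but to skip the 2-month vaccines there.

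Section 6.9 arranges 2-month vaccines at Day 14 only for infants who did not have them before Visit 1. It does not say which arms this concerns. Its schedule table shows one order only: rotavirus vaccine at 6 to 12 weeks, then 2-month vaccines two weeks later.

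Exclusion 3 in section 4.3 rules out "receipt of any vaccine except initial HBV (must have at least 28 days between HBV and Visit 1 to be included".

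On timing, section 5.1 states: "After consent is obtained, infant will be randomized into one of four study groups". The enrolment list in 5.3 has staff "randomize to study group and inform parent of result of all routine vaccines or rotavirus vaccine alone (not specific rotavirus vaccine type", and 6.1 also places randomisation before Visit 1. At Visit 1, 5.3 requires that "inclusion and exclusion criteria will be reviewed to determine if child still meets criteria for study", listed ahead of the MRI and vaccination. At enrolment staff also "collect contact information including the primary care provider of infant and the date of 2 month check up if known".

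**The concern.** A parent who follows the first order in 5.2 brings to Visit 1 an infant who fails exclusion 3. By then the infant has been randomised and the parent knows the arm type. The plan does not say what happens next, and both outcomes are poor.

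- **The infant is excluded.** There is no baseline MRI, so no change in ileum thickness can be computed. Replacement under section 4.4 can restore the count but not the randomised comparison.
- **The infant is dosed anyway.** An arm meant to isolate rotavirus vaccine then contains recently vaccinated infants. Section 2.3 says routine vaccines could add to or disturb the inflammatory response under study.

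The with/without contrast is part of the four-group primary analysis in 10.3, and it also informs whether arms are pooled by vaccine type.

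**Working it through.** The plan states no figure on this point, so the check compares texts and then tests whether the sequence can occur.

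**1. The two rules.** Under 5.2, routine vaccines may come two weeks or more before rotavirus vaccine in the RV-alone arms. Under exclusion 3, the only vaccine allowed beforehand is the initial HBV, at least 28 days before Visit 1. DTaP, Hib, IPV and PCV13 are all barred. An HBV dose given with them 14 to 27 days before Visit 1 also fails the 28-day interval. The two rules cannot both be followed under the first order. The second order satisfies both.

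**2. Whether exclusion 3 applies only at enrolment.** It does not. Its HBV interval is counted to Visit 1, the criteria are reviewed again at Visit 1, and the reviews at Visits 2 and 3 name vaccine receipt explicitly.

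**3. Whether the failure comes after randomisation.** Sections 5.1, 5.3 and 6.1 place randomisation before Visit 1. Appendix 1 marks it at both recruitment and Day 0, but the 5.2 clause is addressed to parents of infants who are already randomised.

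**4. Whether the sequence fits the age limits.** Inputs are the 6-week minimum age for the routine vaccines (6.9 table), recruitment below 11 weeks (Appendix 1), and Visit 1 at "6 wks to- 12 wks, 6 days" (Appendix 1).

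- Earliest: 6 × 7 = day 42; 42 + 14 = day 56.
- Routine vaccines at 2 months (taken as about day 61): 61 + 14 = day 75.
- Latest recruitment: 11 × 7 − 1 = day 76; 76 + 14 = day 90 = 12 × 7 + 6, the Visit 1 ceiling.

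The sequence is therefore possible. At the recruitment limit it needs routine vaccination on the day of recruitment and leaves no slack.

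**5. Size per infant.** With the maximum of 150 infants allocated 1:1:1:1, the RV-alone side has about 150/2 = 75 and each arm about 150/4 = 37.5.

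- One infant lost: 1/75 = 1.3% of the RV-alone side, or 1/37.5 = 2.7% of one arm.
- k infants lost: k/75 of the RV-alone side. The documents give no value for k, and k = 0 is possible.

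**6. Age at 2-month vaccines if rotavirus vaccine always comes first.** The latest case is 90 + 14 = day 104 = 14 × 7 + 6, that is 14 weeks 6 days. This is 104 − 61 = 43 days after about 2 months of age.

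**The case against.** The strongest reply is that the plan already prevents this. Exclusion 3 is explicit. Staff record the 2-month check-up date, if known, at the visit where they schedule Visit 1, so they can put Visit 1 first. Appendix 1 marks the criteria for review at recruitment, the day before Visit 1 and Visit 1. The only schedule table is rotavirus-first. Section 5.2 does not say that parents choose the order. The parent's written Visit 1 instructions (Appendix 5) are not in the document as available for review and may tell RV-alone parents to hold routine vaccines. All of this stands, and it lowers the practical risk. It does not reconcile 5.2 with exclusion 3. An infant vaccinated before enrolment would simply fail screening, so on neither timing does the first order describe an eligible infant.

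The 6.9 clause is weak support. It names no arm and may be loose wording meant to separate infants vaccinated at Visit 1 from the rest.

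A reader might infer more than the documents support:

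- **That the RV-alone arms will lose infants, or that the primary contrast is biased.** No passage says how often this order would be followed, and none links vaccination order to change in ileum thickness.
- **That the share of eligible Visit 1 days compatible with routine-first measures the exposure.** It counts calendar days, not infants, and depends on the assumed age at routine vaccination.
- **That RV1 alone versus RV5 alone is compromised.** Both arms receive the same instruction.
- **That exclusion is the only outcome.** If exclusion 3 is the out-of-date text, staff might dose the infant instead.

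**Conclusion.** The plan is wrong as written: the instruction to RV-alone parents contradicts a stated eligibility rule, and no exemption links them. Only the routine-first order is affected. An RV-alone infant who takes routine vaccines between randomisation and Visit 1 would either be lost before the baseline MRI or enter the arm in breach of exclusion 3.

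Because 5.2 asks only the with-routine arms to hold the 2-month vaccines, any such loss could fall unevenly on the with/without contrast. That remains conditional, since Appendix 5 could contain a hold for the other arms. No bias figure is justified. The text supports only the per-infant size above, which assumes full enrolment of 150 and near-equal arms; simple randomisation makes the arm sizes approximate.

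Severity is minor to moderate. The contradiction itself is certain, its practical effect is unknown, and correcting it is cheap.

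**What to change.** Preferred change:

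- Delete the routine-first clause from 5.2.
- State in 5.2 that infants in all four arms receive no routine vaccines between enrolment and Visit 1, and schedule Visit 1 around the recorded 2-month check-up date.
- Reword 6.9 so that 2-month vaccines are arranged at Visit 3 for the RV-alone arms, without the condition about vaccines already given.
- Check that Appendix 5 and the parent script say the same.

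This adds no visits, infants or analyses. Its cost is later 2-month vaccines for RV-alone infants, at day 104 in the latest case. The 6.9 table already implies this, but it sits less well with inclusion criterion 7, which expects those vaccines on the recommended schedule.

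If routine-first was intended, exclusion 3 needs an explicit exemption for the RV-alone arms. The cost is that recent routine vaccination could affect baseline imaging and cytokines in those arms only. That is why deletion is preferred.

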## 5.3 Study Visits

### Enrollment/Recruitment Visit

- review inclusion/exclusion criteria and medical history
- obtain informed consent
- obtain a release to get medical information from the primary care provider
- collect contact information including the primary care provider of infant and the date of 2 month check up if known
- if refuses study, record refusal reason on screening log
- sample collection instructions
- distribute sample collection supplies
- review MRI and ultrasound prep
- randomize to study group and inform parent of result of all routine vaccines or rotavirus vaccine alone (not specific rotavirus vaccine type)
- schedule visit 1  
give written instructions for Visit 1 to parent (Appendix 5) **Reminder Call 1 (day prior to Visit 1)**
- review sample collection instructions
- review MRI/ultrasound prep  
review time, date and location of Visit 1 **Visit 1 (Day 0-Vaccine Administration)**
- contact information will be reviewed and updated if necessary
- inclusion and exclusion criteria will be reviewed to determine if child still meets criteria for study
- temperature will be recorded prior to immunization; axillary temperature must be <100.4° F prior to administration of vaccines
- breast milk specimen brought from home if mother is breast feeding or can be collected at the visit if needed
- saliva specimen collected for human blood group antigen testing
- baseline stool specimen (brought from home) before receiving the rotavirus vaccine
- MRI to assess intestinal anatomy and motility
- Ultrasound of abdomen to assess intestinal anatomy
- baseline blood specimen for cytokine testing and maternal antibody testing (IgG)
- The Vaccine Information Sheet (VIS) will be provided to parents/guardians for all vaccines administered.
- The study product administrator, who is licensed to administer the vaccine (e.g., MA, LPN, RN, NP, PA, or MD), will orally administer the rotavirus vaccine as indicated in the randomization code
  - if the infant vomits after receiving the vaccine, in accordance with AAP and ACIP recommendations, the vaccine will not be readministered but time of vaccine administration and vomiting will both be documented.

- For infants randomized to receive other vaccines as part of the study, the study product administrator, who is licensed to administer the vaccine (e.g., MA, LPN, RN, NP, PA, or MD), will administer the vaccines, according to standard practice: Pentacel (DTaP, Hib and IPV combination), Prevnar (PCV13) and HBV, in addition to the rotavirus vaccine. If one of these is not available we will replace it with another equivalent licensed vaccine.
- Memory aide will be reviewed with the parent and the parent will demonstrate ability to take temperature and will be instructed in the collection of reactogenicity, adverse event, fever and concomitant medication administration data for 14 days after vaccination. Parent/guardian will be given a thermometer to use for daily axillary temperature recording
- distribution of supplies for daily stool collection for 14 days with instructions for storage and return
- written instructions (Appendix 6) will be given to the parent with the date, time and location for Visit 2 and need for infant to be NPO (nothing to eat or drink) for 3 hours prior to appointment and to return with daily stools collected
- payment for time and travel will be provided for the study procedures
- study personnel will complete the case report form CRF

### **Reminder Call 2 (Day 3 +2 days)**

- review sample collection instructions
- review MRI/ultrasound prep
- review time, date and location of Visit 2
- review memory aide with parent/guardian

### **Visit 2 (Day 5 +/- 1 day) Post-Vaccination)**

- contact information will be reviewed and updated if necessary
- inclusion and exclusion criteria will be reviewed to determine if child still meets criteria for study (no vaccines given since last visit)
- MRI to assess intestinal anatomy and motility
- ultrasound to assess intestinal anatomy
- submission of daily stool specimens collected
- blood collected for cytokine testing
- memory aide will be reviewed with the parent and the parent will demonstrate ability to take temperature and will be instructed in the collection of reactogenicity, adverse event, fever and concomitant medication administration data for remaining study period
- distribution of supplies for daily stool collection with instructions for storage and return
- payment for time and travel for study procedures
- written instructions (Appendix 7) given to the parent with the date, time and location for Visit 3 and need to return with the collected daily stool specimens and memory aide
- study personnel will complete the Case Report Form (CRF)

